4.1 Aim(s)

- To establish the feasibility of delivering ILA during acute stroke rehabilitation.
- To test the integrity of the study protocol (pilot)
- To generate data to inform the design of a Phase III trial.

4.2 Study Design

This is a multicentre, assessor blind, cluster randomised controlled pilot trial, with embedded feasibility study. It also includes a nested qualitative evaluation, designed to explore the views of participants and therapists.

A cluster randomised design is being used, as it is the only way to protect against contamination between treatment arms. Information about the exact detail of the ILA will only be shared once randomisation has taken place, with the sites who will be delivering the intervention. Standard care clusters will not have access to the trial materials (e.g. treatment manual), or details about the specific elements of the intervention.

4.3 Understanding and Describing Baseline

In order to understand current practice within each unit, we will conduct a small observational study at the beginning of the trial. Between 6-10 standard care treatment sessions will be video recorded at each site. This will take place **before randomisation** has taken place, and therefore before clinicians have received any training. We will use non-probability sampling to video record between 6-10 patient-therapist pairs (exact number to be agreed locally, depending on the size of the Unit/Team). Each recorded session will involve a different patient-therapist pair, but the individual patients/therapists may be recorded more than once. Therapists will be asked to continue with a routine therapy session, aimed at improving sit to stand, stepping or gait.

We will analyse the content of these recorded sessions using a previously validated method [1]. This will give us an indication of the likely content of standard care in each participating organisation, and will help us to tailor the required training (for the intervention sites). By later comparing the collective content of these recordings to those taken during the trial, we will also get insight into the differences between the trial interventions and standard care.

These video recordings will be made before recruitment to the pilot trial commences. Patients involved in this stage will not be recruited into the pilot study. A separate Participation Information Sheet and consent form is provided.

4.4 Recruitment of Clusters

4.4.1 Eligibility Criteria for Clusters (Stroke Units)

Criteria for stroke unit eligibility are - a dedicated unit that

- i) routinely admits patients with acute stroke; and
- ii) has a dedicated therapy (OT/PT) service for at least 5 days per week.

Stroke Units do not need to provide hyper-acute care to be involved, but must admit patients within 5 days of stroke onset. We aim to recruit 6-8 Stroke Units to the trial.

4.4.2 Consent for Clusters

Written informed consent will be obtained by the cluster guardian (senior clinician) at each site.

The cluster guardian is consenting for the *Stroke Unit* to take part in the trial, and to be randomised to either ILA or standard care. Within clusters, individual patients who meet the eligibility criteria will be approached, and will be invited to take part in the trial, for which they will provide informed consent (see 4.5.2).

4.5 Recruitment of Individual Participants

4.5.1 Eligibility Criteria for Participants

Inclusion criteria

- Clinical diagnosis of stroke; presenting with hemiplegia
- Within 14 days of stroke onset
- Medically stable
- Able to
 - tolerate daily therapy for a minimum of 30 minutes per session
 - sit for more than 5 seconds without support
 - understand and follow 1 stage commands

Exclusion criteria

- Previous stroke with residual impairments
- Other neurological diagnosis (e.g. PD, MS)
- Clinically relevant pre-morbid disability levels

4.5.2 Consent for Patient Participants

Individual participant informed consent will be taken for participation in the trial. Participants are consenting to receive their rehabilitation using the assigned approach (ILA or standard care), and for collection of data, and completion of additional assessments.

The Easy Read version of the PIS will be used to facilitate a conversation with any potential participant who finds the format of the standard PIS difficult to follow/digest. It is intended as a conversation support tool, to ensure that information about the trial is available in an accessible format for all patients, but particularly those with an impairment of communication or cognition.

All new stroke admissions will be screened for eligibility within 72 hours of admission. Those that meet the criteria will be provided with verbal and written information, which they will be given 24 hours to consider. Those willing to participate will be asked to sign a consent form.

There may be individuals who do not meet the inclusion criteria at the beginning of their Stroke Unit stay, but regain enough function to meet the criteria at a later date. We will continue to monitor potential participants, and will recruit up to 14 days post stroke, if eligibility changes.

The process of recruitment and consent will be led by the research practitioner(s) at each site. Recruitment will take place across an approximate period of four-months at each Unit.

4.5.3 Consent for Participants Deemed to Lack Capacity

Following stroke, is it likely that a proportion of potential participants will be unable to independently make a decision about taking part in the trial (i.e. lack capacity), but otherwise meet the inclusion criteria. This is particularly relevant in the early phase following stroke, where capacity may be borderline or fluctuating, but the person is otherwise engaging in their rehabilitation. For example, an individual may be able to understand the general nature of the research and what participation would involve, but may not fully understand that their data will be used for a research study.

To maintain relevance and ensure generalisability of the findings, it is important to be as inclusive as possible when inviting people to take part. The trial will therefore include participants who do not have capacity to consent to participation. This is deemed appropriate given that:

- Risks associated with the study intervention are negligible
- The trial is not testing a new or novel approach to delivering physiotherapy, but is separating out and comparing approaches that are already in routine use.

4.5.3.1 Process of Assessing Capacity

Potential participants will initially be approached about the trial by a member of the direct clinical team, or a Research Practitioner. If the clinician/research practitioner expresses doubt about the person's ability to provide informed consent for the study, they will notify the Principal Investigator. A capacity assessment will only be completed if the individual meets the criteria, as laid out in the Mental Capacity Act.

The capacity assessment will be completed by the PI at the study site, or a member of the clinical/research team to whom they have delegated responsibility (such as a Research Practitioner or Consultant Physician). The person to whom responsibility had been delegated must have up to date GCP training and have a detailed understanding of the trial protocol. They will be listed on the Delegation Log.

Where appropriate, the person completing the capacity assessment may request assistance from a member of the clinical team, such as a Speech and Language Therapist (SLT) or Psychologist, to aid with the assessment. SLT will provide particular expertise to ensure that people with a language impairment as a result of their stroke are given appropriate and individualised support to understand the information that is presented to them, and to communicate their thoughts and wishes. The Easy Read version of the PIS will be used to support this process.

Irrespective of whether or not someone has capacity, the views expressed by the person will be given precedence when deciding whether or not to proceed. In people who are deemed to lack capacity, any views that are expressed through the facilitated conversation will be given priority when deciding whether or not to pursue a consultee declaration. For example, if the patient expresses anxiety about any part of this process, such as being video recorded, then we will not proceed with seeking a consultee declaration. We will not enrol anyone in the trial who communicates that they do not wish to participate in any aspect of the study.

The capacity assessment will be documented in the patient's medical notes.

[figure not shown]

Figure 1: Recruitment Process for Individuals Lacking Capacity

4.5.3.2 Process for Gaining a Consultee Declaration

If a potential participant is deemed unable to consent to the study (i.e. they lack capacity), then a personal consultee (usually the next of kin) will be asked to consider whether they would be willing to provide consent on their behalf, based on the presumed wishes of the potential participant.

The full version of the Participant Information Sheet will be shared with the identified consultee, along with the Easy Read PIS. If they are willing to do so, they will be asked to sign the consultee declaration form, on behalf of their relative/friend.

In the event that a personal consultee cannot be found for someone who is deemed to lack capacity, a professional consultee would not be used. In these circumstances, the person lacking capacity would not be able to participate in the study.

At all times, the wishes of the participant will be upheld. For example, they will not be video recorded if they express that they do not wish for this to happen.

4.5.3.3 Process if a participant regains capacity during the study

It is feasible that a participant who did not have capacity to provide informed consent at the beginning of the study, regains the ability to do so at some point during the study. The therapists who are delivering the treatment interventions, as well as the research team, will be briefed with regards to this. They will be asked to inform the Research Practitioner and local PI if they feel that a participant's ability to consent has changed. This will then be reassessed. If, at this point, the person is deemed to have capacity to make a decision regarding participation in the research, they will be provided with the study information and will be supported to make this decision. If they opt to withdraw from the study, they can do so, without consequence. Data collected up to this point will be included in the final analysis, unless the individual explicitly asks for it not to be.

Therefore, the Consultee Declaration only applies for as long as the participant lacks capacity. Stroke teams manage issues relating to capacity on a frequent basis, and are therefore typically very aware of the principles of the Mental Capacity Act, capacity assessments and informed consent.

4.5.3.4 Process if a participant loses capacity during the study

[figure not shown]
Although unlikely, a participant who gave informed consent at the point of recruitment, may lose capacity during the course of the research. It is likely that any loss of capacity at this stage reflects medical instability - such as a further stroke, or an infection.

The study will adhere to the principles, as laid out and defined in the Mental Capacity Act (2005). At the time of the person consenting to the trial, they have expressed a wish to participate. Therefore, the person will remain in the study, as long as it is appropriate clinically, and there is no observable or communicated evidence that they do not wish to continue.

If the individual is communicating that they do not wish to continue in the trial, or are demonstrating an unwillingness to participate in any of the trial interventions (e.g. assessments, video recording, or therapy treatment sessions), then they will be withdrawn

The most likely cause of loss of capacity is a further stroke, or another medical event. In these circumstances, then (irrespective of capacity) the person will not be clinically appropriate to remain in the trial, and will be withdrawn.

4.6 Trial Flowchart

4.7 Intervention

All mobility focussed rehabilitation sessions will utilise the ILA, as usual care. This includes rehabilitation (delivered by a physiotherapist, occupational therapist or therapy assistant) that focusses on sitting, sit to stand, standing, stepping, transfers and walking. The content of therapy will be based on the treatment guidelines and intervention manual, which have been developed by an international expert group (using Delhi methodology). As this is a clinically grounded, pragmatic trial, therapists will have freedom to tailor the specific content of each treatment session to patient need, whilst remaining true to the ILA. Other therapy interventions, such as upper limb rehabilitation, will be provided as usual. Whilst the content of this additional therapy will not be monitored, the quantity of other therapy, outside of the trial interventions, will be recorded and compared between groups. Frequency of treatment will be based on the usual practice of the treating hospital. The actual number of sessions received by each participant will be recorded.

Specific details relating to the IMPS intervention will be shared with intervention sites, once randomisation has taken place. Standard care sites will continue to delivery rehabilitation as normal, but will be asked to recruit eligible patients for data collection. An overview is given in table 1.

	Control Group Standard Care*	Experimental Group Implicit Learning Approach
Quantity and Frequency of Coaching Statements (Instructions and Feedback)	HIGH 
 Instructions given at the beginning and throughout the task (i.e. during practice) Feedback given during task practice – at least once for every 5 repetitions of any given task 	LOW 
 Instructions only given at the beginning of task practice Feedback or further instruction avoided throughout task practice
Focus of Attention	INTERNAL Direct attention to the action itself. Use the term “focus on [a reference within the body]”. Example: “Bend your knee and lift your foot onto the block. Focus on moving your leg”	EXTERNAL Direct attention to the effects of the action. Use the term “focus on [a reference in the environment]” Example: “Step onto the marker on the block. Focus on the marker”
Task Set Up	Activity and environment set up to facilitate a focus on the person – i.e. without using external reference points/feedback.	Activity and environment set up to facilitate a focus on the environment – through use of external reference points, markers, audio feedback.

* Guidance for standard care is based on published observational studies describing usual practice in stroke rehabilitation [1, 10, 11].
 
Table 1: Overview of Intervention
		

4.8 Control

Standard care, as per usual working practice for the stroke unit. Control stroke units will have minimal contact with the research team, other than for data collection. They will be aware of the broad aims of the study, but not the specific detail of the intervention.

4.9 Duration of Treatment

Patients will be recruited as soon as eligible, and up to 14 days of stroke onset. Trial interventions will be delivered for the duration of each participant's inpatient stay, as deemed appropriate by the treating team. This approach is pragmatic and will ensure that the intervention can be fitted into the current care pathway, but accepting that discharge will be at different times for different patients.

4.10 Training for Intervention Sites

For sites randomised to the intervention arm, all physiotherapists, occupational therapists and therapy assistants will be trained in the ILA. Training is anticipated to last no more than 3 hours. Additional training sessions will be offered if new members join the team during the recruitment phase. A manual including written, photographic and video resources will demonstrate how to adapt standard care interventions to the ILA. Therapists will be able to refer to the manual throughout their involvement in the study.

Whilst the wider multidisciplinary team (e.g. nurses, doctors, other AHP's) will not specifically be asked to change their approach with patients, those at intervention sites will be invited to attend a short education session to raise their awareness of the trial, and will be provided with written information about the study, and the concepts under investigation. As these professions wouldn't typically be analysing movement or giving specific instructions/feedback, this level of engagement is deemed appropriate and realistic.

The therapy team will be encouraged to give the MDT (particularly nurses) specific guidance about how to instruct an individual patient during movement (as part of a manual handling care plan, and in line with the ILA approach). These awareness raising sessions will support the MDT to understand and follow through these instructions.

As part of the training, clinical staff will be reminded of the options to withdraw participants from the study, should there be concerns about the impact the ILA has on their recovery (see 7.1.1).

4.11 Bias Protection

Outcome assessors will be blind as to the intervention group. Video recording of outcome measures will be used to achieve this. Participants will be blind as to whether their Stroke Unit is providing control or intervention. Whether or not participants have guessed their treatment arm will be explored in the qualitative interviews.

4.12 Measures

Measures will be performed and recorded by the stroke research practitioner(s), or designated clinician, at each site. As the research practitioner will not be blind to the intervention arm, all measures will be video recorded, and later scored by a blinded second assessor. Frequent measures are required to understand *rate* of change. Outcome measures have been selected with consideration of international recommendations for measurement of sensorimotor recovery in stroke [12].

At baseline:

- Movement Specific Reinvestment Scale (Self-Report Questionnaire) (MSRS)

At baseline, week 2, week 4, week 6 post enrolment (or up to the point of discharge):

- Fugl Meyer – motor leg sub section
- Modified Postural Adjustment in Stroke Scale (SwePASS)
- Modified Rivermead Mobility Index (mRMI)
- Able to sit for 1 minute unsupported?
- Able to transfer from bed to chair independently?
- Able to walk 10m independently?

At point of discharge

- Discharge destination and care requirements immediately on discharge (number of care visits per day multiplied by the number of carers required)
- Fugl Meyer – motor leg sub section
- Modified Postural Adjustment in Stroke Scale (SwePASS)
- Modified Rivermead Mobility Index (mRMI)
- Able to sit for 1 minute unsupported?
- Able to transfer from bed to chair independently?
- Able to walk 10m independently?
- Movement Specific Reinvestment Scale (MSRS)

At 3 months post enrolment:

- Fugl Meyer – motor leg sub section
- Modified Postural Adjustment in Stroke Scale (SwePASS)
- Modified Rivermead Mobility Index (mRMI)
- Able to sit for 1 minute unsupported?
- Able to transfer from bed to chair independently?
- Able to walk 10m independently?
- Modified Rankin Scale (mRS)
- EQ-5D
- Movement Specific Reinvestment Scale (MSRS)

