12.5	Movement Specific Reinvestment Scale.....	29

1 Study Synopsis

Title	A pilot cluster randomised controlled trial, of an implicit learning approach (ILA) versus standard care, on recovery of mobility following stroke.
Protocol Short Title/Acronym	Implicit Learning in Stroke Study (IMPS)
Protocol Version Number and Date	V2 24/09/2018
Study Phase	Pilot (with embedded feasibility)
Study Hypothesis	None
Study Duration	24 months
Methodology	Cluster (Stroke Unit) randomised controlled pilot trial, with nested qualitative exploration of participant and therapist views.
Sponsor Name	Royal Bournemouth and Christchurch Hospitals NHS Foundation Trust and University of Southampton
Chief Investigator	[name]
REC Number	[to be added]
Medical condition under investigation	Stroke
Primary Objective	To establish the feasibility of delivering an ILA during acute stroke rehabilitation (fidelity), and to test the integrity of the study protocol (pilot).
Secondary Objective(s)	To generate data to inform the design of a Phase III trial – including: 
 • Identification of training requirements of clinical teams delivering ILA • Identification of most appropriate outcome measure • Estimation of expected rates of recruitment and retention • Estimation of effect size to enable future sample size calculation • Therapist and patient perceptions of the approach
Number of Clusters	6-8
Number of Participants	60
End Point	3 months post stroke
Main Inclusion Criteria	Clinical diagnosis of stroke; presenting with hemiplegia Within 14 days of stroke onset Medically stable Able to 
 • tolerate daily therapy for a minimum of 30 minutes per session • sit for more than 5 seconds without support • understand and follow 1 stage commands
Primary Outcome Measure	Change in modified Rivermead Mobility Index score at 4 weeks.
Statistical Methodology and Analysis	Within group change scores for all outcome measures with 95% confidence interval

2 Abbreviations

AI	Adverse Incident
HASU	Hyperacute Stroke Unit
ILA	Implicit Learning Approach
FM-LL	Fugl Meyer Assessment – Lower Limb Section
MDT	Multidisciplinary Team
mRMI	Modified Rivermead Mobility Index
MSRS	Movement Specific Reinvestment Scale
SU	Stroke Unit
SwePASS	Modified (Swedish) Postural Adjustment in Stroke Scale

3 Background and Rationale

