4.16 Analysis

Data will be stored and managed using SPSS. Statistical support will be provided by the University of Southampton. Double data entry will be used for paper-based assessments.

The unit of analysis is the individual patient. As this is a pilot study, analysis will primarily be descriptive. Descriptive methods will be used to estimate feasibility of factors relating to the protocol, such as recruitment (proportion of eligible people who consent to the study) and retention (completion of outcome measures at 4 weeks).

Fidelity of the interventions will be established by comparing the number and type of coaching statements delivered to each group. We will describe the mean number of coaching statements per person (and the breakdown of these statements as externally- or internally-focussed) in each group. While we expect large differences, we will not formally test the difference as the study is not designed to do so; we will instead provide an estimate of the difference with corresponding 95% confidence interval. Differences in outcome and potential effect size for the Fugl Meyer, SwePASS and mRMI will be calculated using confidence interval estimation.

5 Process Evaluation

To enable us to understand patient and therapist perceptions and experiences of the ILA, will we be inviting a sub-set of participants to take part in a qualitative evaluation of the ILA.

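### Live and blinded video scores of the mRMI and SwePASS are never compared, and the video assessor is not masked to visit, although the pilot is meant to test the protocol and choose an outcome measure.

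*Combined protocol and SAP*

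**What the plan says.** Section 4.2 describes the design: "This is a multicentre, assessor blind, cluster randomised controlled pilot trial, with embedded feasibility study". Section 4.11 states: "Outcome assessors will be blind as to the intervention group", and on the means: "Video recording of outcome measures will be used to achieve this".

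Section 4.12 says who does the testing: "Measures will be performed and recorded by the stroke research practitioner(s), or designated clinician, at each site". It gives the reason for filming, "As the research practitioner will not be blind to the intervention arm", and the consequence: "all measures will be video recorded, and later scored by a blinded second assessor".

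The synopsis names change in mRMI at 4 weeks as the primary outcome and within-group change with a 95% confidence interval as the analysis. Its objectives include testing the integrity of the protocol and "Identification of most appropriate outcome measure". Section 4.16 adds a between-arm element: "Differences in outcome and potential effect size for the Fugl Meyer, SwePASS and mRMI will be calculated using confidence interval estimation".

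Neither the synopsis nor 4.16 names the source of the score, and neither mentions a comparison of live with video scoring. The one coherence check, in 4.15, sets films of treatment sessions against the written treatment records. It does not involve outcome scores.

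**The concern.** Blinding by video is the plan's main protection against assessor bias, and it takes work: every assessment is filmed, transferred and scored again. A pilot that tests its own protocol should learn whether that work changes the scores, and which scale gives the same answer in the room and on film. The paired scores that would show this very probably exist, but no analysis uses them.

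The scales leave room for judgement where it matters. Level 3 of the mRMI (Appendix 12.2) turns on supervision or verbal instruction, and the SwePASS notes (Appendix 12.1) grade support that may be verbal, tactile or supervisory. Verbal instruction is what the intervention changes (Table 1).

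The second gap is masking of visit. An assessor who is blind to arm but knows that a clip is from week 4 may expect improvement on baseline. If that expectation is equal in both arms, it tends to cancel from a between-arm difference. It does not cancel from a within-group change, which is the analysis in the synopsis.

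**Working it through.** **Which score is the outcome.** Section 4.2 calls the trial assessor blind. Section 4.11 makes outcome assessors blind by means of video. Section 4.12 says that video is needed because the research practitioner is not blind. Together these point to the video score. What 4.16 lacks is the explicit statement and a rule for an assessment without a usable clip.

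**Whether a live score exists.** Section 4.12 has site staff performing and recording the measures and calls the video assessor the second one. The mRMI form has fields for assessor and score, and 4.16 plans double entry of paper-based assessments. A retained live score is the natural reading, but it is nowhere stated.

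**How many pairs.** There are six assessment points: baseline, weeks 2, 4 and 6, discharge and 3 months. So 60 × 6 = 360 pairs per scale is the ceiling. Fewer will arise, because the measures at weeks 2 to 6 run only up to discharge.

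**The plan's own figure.** Section 4.13 gives 60 participants in 6-8 clusters, 7-10 each. 60/6 = 10 and 60/8 = 7.5, so this reproduces with the lower end rounded down (8 × 7 = 56). The documents contain no power calculation, SD or intracluster correlation.

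**Precision of the arm difference in live-minus-video.** Assumptions: 30 per arm, one pair each, k equal clusters split evenly between arms, m = 60/k, and intracluster correlation ρ of the discrepancy. In units of the paired-difference SD:

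half-width = t(0.975; k − 2) × √[(2/30) × (1 + (m − 1)ρ)]

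- k = 8, m = 7.5, ρ = 0.05: 1 + 6.5 × 0.05 = 1.325; t on 6 df = 2.447; 2.447 × √0.0883 = 0.73.
- k = 6, m = 10, ρ = 0.05: 1 + 9 × 0.05 = 1.45; t on 4 df = 2.776; 2.776 × √0.0967 = 0.86.

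| Assumed ρ | 8 clusters | 6 clusters |
|---|---|---|
| 0 | 0.63 | 0.72 |
| 0.05 | 0.73 | 0.86 |
| 0.10 | 0.81 | 0.99 |
| 0.30 | 1.09 | 1.38 |

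A normal quantile at ρ = 0.05 would give 0.58 to 0.61, which is too narrow with so few clusters.

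On the mRMI (eight items scored 0-5, so 0-40), an assumed paired-difference SD of 1 to 3 points gives half-widths at ρ = 0.05 of 0.7 to 2.2 points with 8 clusters and 0.9 to 2.6 points with 6. Raters belong to one site, so ρ for the discrepancy may well exceed 0.05. At ρ = 0.30 and SD 2 the half-width is 2.2 to 2.8 points. Missing week-4 assessments widen all of these.

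**The case against.** The strongest reply is that the blinding plan is sound as designed and that an inter-rater table is an optional extra in a pilot whose analysis is mainly descriptive. Much of this stands, and it limits the point in four ways.

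First, a reader might infer that the plan leaves open which score is the outcome, or that unblinded scores will fill gaps and be reported as blinded. The documents do not support either. Sections 4.2, 4.11 and 4.12 point to the video score, and no section plans substitution. What is absent is clarifying detail.

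Second, a reader might take live-minus-video as a direct measure of assessor bias. It is not. The raw gap mixes knowledge of arm with scoring in the room versus from film. The arm difference in the gap is closer to the question, but units are allocated to arms and each unit's own staff do the testing. Every live rater therefore sees one arm only, with 3-4 units per arm under an even split, and leniency of individual raters cannot be separated from an effect of knowing the arm. Both scores also rate the same performance, so bias in how the test is conducted stays hidden.

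Third, a reader might argue that rater bias would be estimated several times more precisely than the treatment effect. Any such multiple is only the ratio of two SDs that the documents do not give, so it carries no weight.

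Fourth, video scoring cannot serve every measure alone. The Fugl-Meyer form (Appendix 12.3) calls for elicited reflexes, palpated tendons and applied resistance. This is why the comparison is best confined to mRMI and SwePASS.

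The reply does not remove the core: paired scores that bear on two stated objectives go uncompared, and nothing masks visit. The documents do not say that clips carry labels, so masking is a safeguard against a possible problem, not a correction of a known one.

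**Conclusion.** The point holds as a cheap improvement. The blinded video score is the intended outcome by clear implication. No section compares it with the live score, and no section masks visit or clip order, while the synopsis relies on within-group change.

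The comparison would give useful descriptive information on agreement for each scale. For bias by arm it would be coarse: a half-width of about 0.73 to 0.86 paired-difference SDs for 8 to 6 clusters, which could exclude only a large arm effect on scoring. This rests on the assumptions of 30 per arm with paired scores, equal clusters, an intracluster correlation of 0.05, and live scores being kept as data.

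**What to change.** **Section 4.16, agreement.** For mRMI and SwePASS, report descriptively the live-versus-video agreement (intraclass correlation and limits of agreement). Report the arm difference in mean live-minus-video with a cluster-level 95% confidence interval (t on clusters minus 2 df). Use the results in choosing the Phase III measure. State three limits beside the table: scoring mode and rater effects are mixed; live raters are nested within units and arms; bias in the conduct of the test cannot be detected.

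**Section 4.12, masking.** Give the video assessor clips in random order with unit and visit labels removed. Confirm that site staff record a live score that is kept as data.

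**Section 4.16, clarification.** Name the video score as the main-analysis outcome for mRMI and SwePASS, use live scores only in a sensitivity analysis, and report missing or unusable clips by arm. Say whether an assessment with a live score but no usable clip counts towards retention at 4 weeks. State separately which Fugl-Meyer items need input from the site.

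**Cost.** One extra table and some clip handling, with no new staff or visits. Scoring must wait until enough clips exist to shuffle, and the main analysis loses the few assessments without a usable clip.
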